Study Design and Treatment	This study is a randomized, double-blind, placebo-controlled SAD study. There are 3 planned dose-level cohorts (Cohorts 1-3). Each dose-level cohort will consist of 8 subjects (6 active + 2 placebo), who will be treated under fasted conditions. The subjects in the highest tolerated dose-level cohort will also be administered ISLA101 under fed conditions, in a cross-over manner (Cohort 4). Proposed doses are 300, 600, and 900 mg/m² (equivalent to 8.1, 16.2, and 24.3 mg/kg). Each subject will be allocated to 1 dose level only.  The study will include a 5-day stay in the clinical research unit followed by a final safety follow-up visit at Day 8.  An independent Safety Review Committee (SRC) will review available safety data up to 96-hours post-dose for subjects enrolled in each dose-level cohort. After safety review, the dose level may be escalated to the next planned or lower than

planned dose level, de-escalated to an intermediate dose level, or repeated at the same dose, if needed.

The first 3 dose-level cohorts will be treated under fasting conditions. A single dose of study drug will be administered on the morning of Day 1, after an overnight fast of approximately 10 hours, followed by an additional 4-hour fast after dosing. Study drug will be taken with up to 8 oz/240 ml of water. Water will be allowed ad libitum except the interval from 1 hour before to 1 hour after dosing.

Following review of the safety data of the highest tolerated dose level, the subjects enrolled in this dose-level cohort will be recalled to evaluate the PK of ISLA101 dosed under fed conditions (Cohort 4; 8 subjects). These data will support a planned Phase 2 study. Subjects will be informed and will be provided a consent form prior to the participation in the food effect cohort (Cohort 4) of the study.

Subjects in Cohort 4 will be dosed after a meal. They will fast overnight for at least 10 hours and will then consume a high-fat, high-calorie meal prior to administration of study drug, as outlined in the FDA's Guidance for Industry- Assessing the Effects of Food and Drugs in INDs and NDAs – Clinical Pharmacology Considerations. The study drug should be administered approximately 30 minutes after start of the high-fat meal. No food consumption will be permitted for at least 4 hours post-dose. Water will be allowed ad libitum except the interval from 1 hour before to 1 hour after dose.

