# 10.4 Disposition and Demographics

Subject disposition will be summarized and will include all subjects who have received one dose of study drug in the safety population, subjects in the PK population, and number and percent of subjects who complete or prematurely discontinue from the study along with reason for discontinuation. Demographic data will be summarized using descriptive statistics for all subjects who were randomized in this study and took at least 1 dose of study drug.

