**3.1 Safety Population**

This Safety Population will include all subjects who received at least 1 dose of study drug (active and placebo).

The following is reason for exclusion from the Safety Population:

- Subjects did not receive at least one dose of study drug.

The Safety Population will be used for all baseline characteristics, disposition and safety analyses and will be based on actual treatment received if different from randomized treatment.

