**6.1 Subject Disposition and Analysis Sets**

Summary tables will be based on the Safety Population.

The number and percentage of randomized subjects, subjects completing or discontinuing from the study as well as the primary reason for discontinuation will be presented by treatment group and for all subjects overall in the subject disposition table. The denominator for the reason for discontinuation from the study percentage calculations will be the number of subjects that discontinued from the study.

All subject disposition information (as described in Section 4.4.1) will be listed together with the date that the subjects provided informed consent and the date/time of the first study drug administration in the subject disposition listing.

The number of subjects included in the analysis populations defined in Section 3 will be summarized along with the reasons for exclusion from any analysis population by treatment group and for all subjects overall using frequencies and percentages.

In addition, the inclusion/exclusion of each subject into/from each of the defined analysis set will be listed.

The randomization information (where applicable) including the randomized treatment group will be listed.

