## 1 General Statistical Methods

Courier New will be used as font for all output produced in SAS®. The font size for all output will be 8p.

Results presented in table columns will be positioned as follows:

- Alphanumeric values will be left aligned.
- Integer numbers (e.g., counts) will be right aligned.
- Numbers containing fractional portions will be decimal aligned.

In all titles and analysis population names, coordinating conjunctions (and, or), articles (a, an, the) or prepositions will not be capitalized. All other words will be capitalized as well as the first and last words of the title or name.

The footnotes must make provision for the name of the SAS® program used to produce the output and the date and time that the output was created.

Words followed by a designator will be capitalized, for example, Day 1, Subject 3046, Day 10 etc.

Page numbers will be indicated as "Page x of y" at the bottom of each page.

Individual subject listings will be produced for all raw data and a selection of the derived data.

**Tables, Listings and Figures Shells****Sponsor:** Island Pharmaceuticals, Ltd**Protocol Number:** ISLA101-P01-CT001

**Sponsor:** Island Pharmaceuticals Ltd  
**Protocol:** ISLA101-P01-CT001

Table 14.1.1.1 Summary of Analysis Population (Safety Population)

	ISLA101 300 mg Fasted (N=xx) n (%)	ISLA101 600 mg Fasted (N=xx) n (%)	ISLA101 900 mg Fasted/Fed (N=xx) n (%)	Pooled Placebo (N=xx) n (%)	All Subjects (N=xx) n (%)
Safety Population					
Number of Subjects Included	xx (xx%)	xx (xx%)	xx (xx%)	xx (xx%)	xx (xx%)
Number of Subjects Excluded	xx (xx%)	xx (xx%)	xx (xx%)	xx (xx%)	xx (xx%)
Reasons for Exclusion					
Reasons for Exclusion 1	xx (xx%)	xx (xx%)	xx (xx%)	xx (xx%)	xx (xx%)
Pharmacokinetic Population					
Number of Subjects Included	xx (xx%)	xx (xx%)	xx (xx%)	xx (xx%)	xx (xx%)
Number of Subjects Excluded	xx (xx%)	xx (xx%)	xx (xx%)	xx (xx%)	xx (xx%)
Reasons for Exclusion					
Reasons for Exclusion 1	xx (xx%)	xx (xx%)	xx (xx%)	xx (xx%)	xx (xx%)

The Safety Population will include all subjects who received at least one dose of the study drug (ISLA101 or Placebo).

The Pharmacokinetic Population will consist of all subjects in the safety population who have a pre-dose PK sample and at least one post dose analyzable PK sample and at least 1 post-dose analyzable PK sample (quantifiable Plasma concentration).

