Percentage (%) of subjects (n) in each category are calculated based on the number of subjects in the analysis population (N).

Percentage (%) of subjects (n) for the reason for exclusion categories are calculated based on the number of subjects that were excluded from the specific analysis population.

Program Name: xxx.sas, Creation Date Time: YYYY-MM-DD HH:MM

Page 1 of x

Programmer Note:

In the final analysis, the group "ISLA101 900 mg Fasted/Fed" will be replaced by the highest tolerated dose-level cohort. For the "Pooled Placebo" group, the placebo fasted and Fed subjects will be counted once only. Therefore, the number of subjects (N) in Pooled Placebo basically should be 6.

**Tables, Listings and Figures Shells****Sponsor:** Island Pharmaceuticals, Ltd**Protocol Number:** ISLA101-P01-CT001

**Sponsor:** Island Pharmaceuticals Ltd  
**Protocol:** ISLA101-P01-CT001

Table 14.1.2.1 Summary of Subject Disposition (Safety Population)

	ISLA101 300 mg Fasted (N=xx) n (%)	ISLA101 600 mg Fasted (N=xx) n (%)	ISLA101 900 mg Fasted/Fed (N=xx) n (%)	Pooled Placebo (N=xx) n (%)	All Subjects (N=xx) n (%)
Number of Subjects who Completed the Study	xx (xx%)	xx (xx%)	xx (xx%)	xx (xx%)	xx (xx%)
Number of Subjects who did not Complete the Study	xx (xx%)	xx (xx%)	xx (xx%)	xx (xx%)	xx (xx%)
Primary Reason for Early Study Discontinuation					
Adverse Event	xx (xx%)	xx (xx%)	xx (xx%)	xx (xx%)	xx (xx%)
Withdrawal of Consent	xx (xx%)	xx (xx%)	xx (xx%)	xx (xx%)	xx (xx%)
Physician Decision	xx (xx%)	xx (xx%)	xx (xx%)	xx (xx%)	xx (xx%)
Pregnancy	xx (xx%)	xx (xx%)	xx (xx%)	xx (xx%)	xx (xx%)
Protocol Deviation	xx (xx%)	xx (xx%)	xx (xx%)	xx (xx%)	xx (xx%)
Lost to Follow-up	xx (xx%)	xx (xx%)	xx (xx%)	xx (xx%)	xx (xx%)
Sponsor Request	xx (xx%)	xx (xx%)	xx (xx%)	xx (xx%)	xx (xx%)
Other	xx (xx%)	xx (xx%)	xx (xx%)	xx (xx%)	xx (xx%)

Percentage (%) of subjects (n) in each category are calculated based on the number of subjects in the analysis population (N).

Percentages (%) of subjects (n) for the reason of early study termination categories are based on the number of subjects who early terminated the study.

Program Name: xxx.sas, Creation Date Time: YYYY-MM-DD HH:MM

Page 1 of x

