## Listing 16.2.3 Randomization (Safety Population)

Cohort 1: ISLA101 300 mg Fasted

Subject Number	Date of Randomization	Replacement Subject	Randomization Number/Replacement Randomization Number
xxx-xxx	YYYY-MM-DD HH:MM	No	xxxxxxxx
xxx-xxx	YYYY-MM-DD HH:MM	Yes	xxxxxxxx

Program Name: xxx.sas, Creation Date Time: YYYY-MM-DD HH:MM

Page 1 of x

Programmer note:

Repeat for all subjects within the treatment group, and for all treatment groups.

Version and Date: Final Version 1.0, 2023-12-07

Page 65 of 100

Confidential

**Tables, Listings and Figures Shells****Sponsor:** Island Pharmaceuticals, Ltd**Protocol Number:** ISLA101-P01-CT001

**Sponsor:** Island Pharmaceuticals Ltd  
**Protocol:** ISLA101-P01-CT001

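### Disposition and analysis-set tables start from dosed subjects and merge two periods for the recalled cohort only, so one exclusion row is always zero and overall discontinuation is not comparable across columns

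*SAP*

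**What the plan says.** **Base population.** SAP 3.1 assigns disposition to the Safety Population: "The Safety Population will be used for all baseline characteristics, disposition and safety analyses". It gives one reason for exclusion from that population: "Subjects did not receive at least one dose of study drug". SAP 6.1 also bases its summary tables on the Safety Population, yet promises "The number and percentage of randomized subjects, subjects completing or discontinuing from the study as well as the primary reason for discontinuation", together with reasons for exclusion from every analysis population. Protocol 10.4 likewise frames disposition around dosed subjects and asks for the "number and percent of subjects who complete or prematurely discontinue from the study along with reason for discontinuation".

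**Shells.** In SAP Attachment 1 the analysis-set shell is titled "Table 14.1.1.1 Summary of Analysis Population (Safety Population" and has rows for the number excluded from the Safety Population and why, followed by a similar block for the PK Population. The disposition shell, Table 14.1.2.1, starts at "Number of Subjects who Completed the Study" and has no row for randomized subjects. The allocation listing carries the same restriction: "Listing 16.2.3 Randomization (Safety Population".

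**Periods.** Both shells have Fasted columns for two dose levels and one Fasted/Fed column for the third. The programmer notes say that the 900 mg label stands in for whichever cohort proves to be the highest tolerated dose, and that pooled placebo subjects are counted once across both conditions, giving N of 6. Only the recalled cohort repeats confinement and follow-up, to Day 17 instead of Day 8 (SAP 2.3 and 2.5). Entry to the fed period is a fresh decision. The Protocol Synopsis says "Subjects will be informed and will be provided a consent form prior to the participation in the food effect cohort", and eligibility is checked again on Day 9.

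**The concern.** There are two separate problems.

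First, a table that is restricted to dosed subjects cannot report how many were left out for not being dosed. The row looks like a result but cannot take any value except zero. A subject randomized on Day 1 and then not dosed falls outside the stated population of every disposition, analysis-set and randomization output, so allocation cannot be fully reconciled from them.

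Second, safety and tolerability is the primary objective, and a reader will look across the dose columns of Table 14.1.2.1 for a trend in non-completion. One column covers two doses and a second consent decision, and the others cover one dose. A difference between columns may then reflect length of participation instead of dose. Neither document says how to classify a subject who finishes Day 8 and does not enter the fed period. SAP 4.4.1 takes disposition from a single end-of-participation form, so two programmers could code that subject in opposite ways.

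**Working it through.** **1. Reproduce the one count that the shells state.** The inputs are 3 fasted cohorts, each with 6 active and 2 placebo (SAP 2.4). Pooled placebo is 3 × 2 = 6, which matches the programmer note. The total is 3 × 8 = 24. Counting the fed placebo subjects again would give 6 + 2 = 8, which the note rules out.

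**2. The Safety exclusion row.** The table's population is dosed subjects, and the exclusion reason is not being dosed. No subject is both, so the row is 0 in every column. If k of 24 randomized subjects were not dosed, the shell would show 0 of 24 − k. On a randomized base it would show k/24, which is 1/24 = 4.2% for k = 1 and 2/24 = 8.3% for k = 2. The PK Population block is unaffected, because dosed subjects can fail the PK criteria.

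**3. What the merge does to overall discontinuation.** The documents give no discontinuation rate, so the risk p per period is an assumption, taken as equal and independent in the two periods.

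- One-period column: p
- Merged column: 1 − (1 − p)²
- Pooled placebo, with 4 one-period and 2 two-period subjects: [4p + 2(1 − (1 − p)²)]/6
- Chance of at least one discontinuation among 6 active: 1 − (1 − p)⁶ for one period, 1 − (1 − p)¹² for two

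| Assumed p | One-period column | Merged column | Excess (points) | Pooled placebo | At least 1 of 6, one period | At least 1 of 6, two periods |
|---|---|---|---|---|---|---|
| 2% | 2.0% | 4.0% | 2.0 | 2.7% | 0.114 | 0.215 |
| 5% | 5.0% | 9.8% | 4.8 | 6.6% | 0.265 | 0.460 |
| 10% | 10.0% | 19.0% | 9.0 | 13.0% | 0.469 | 0.718 |
| 20% | 20.0% | 36.0% | 16.0 | 25.3% | 0.738 | 0.931 |

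One subject of 6 is 1/6 = 16.7 points.

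**4. Dependence on the missing definition.** Suppose that declining recall counts as not completing, with an assumed refusal rate q. The merged column is then 1 − (1 − p)(1 − q)(1 − p). At p = 5% this is 1 − 0.95 × 0.90 × 0.95 = 18.8% for q = 10%, and 1 − 0.95 × 0.80 × 0.95 = 27.8% for q = 20%.

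As a separate illustration, suppose that all 6 active subjects complete the fasted period and each has an assumed 5%, 10% or 20% chance of not returning or not finishing the fed period. If each such subject is coded as a discontinuation, the chance of at least one is 1 − (1 − 0.05)⁶ = 26%, 1 − (1 − 0.10)⁶ = 47% or 1 − (1 − 0.20)⁶ = 74%. If refusals are not counted and nobody drops out in the fed period, the excess is 0.

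**5. Comparison with the other outputs.** The list of tables in SAP Attachment 1 gives a separate Fasted and Fed version for protocol deviations, concomitant medication, adverse events, laboratory results, vital signs and ECG. Disposition and analysis sets have none.

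**The case against.** The other side has several sound points.

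- The dosed-only base is the protocol's own rule in 10.4, so the SAP has not departed from the protocol.
- Randomization takes place on the dosing day (Protocol 8.1.3.1), after the Day -1 checks, so few randomized and undosed subjects are likely.
- SAP 5.1.5 promises listings of all collected data except screen failures, and Listing 16.2.3 has a replacement flag, so an undosed subject might leave a trace. However, the opening of SAP Section 6 sets listings to the Safety Population by default.
- The merged column is openly labelled and is a correct cumulative count, with each subject counted once.
- AE-driven discontinuation is already reported on fasted-only columns in Tables 14.3.1.7.1 and 14.3.1.8.1, and split by condition in Tables 14.3.1.7.2 and 14.3.1.8.2.
- Table 14.1.2.1 separates adverse events from withdrawal of consent and other reasons.
- Listing 16.2.1.2 gives each subject's completion status, reason and end-of-study day. With 24 subjects, a departure after Day 8 can be read off by hand.

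All of this limits the consequences. It does not remove two facts. SAP 6.1 promises outputs that its own base cannot deliver, and no planned table separates non-AE drop-out by period.

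A reader might infer that discontinuation is biased upward at the highest dose. The documents do not support that. The direction and size depend on a completion rule that they do not state and on fed-period drop-out that they do not quantify. A subject who declines recall could equally be called a completer. The affected column is the highest tolerated dose, not necessarily 900 mg/m², and pooled placebo is itself partly two-period.

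**Conclusion.** The point holds as a matter of reporting.

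- **Exclusions and allocation.** The Safety Population exclusion row in Table 14.1.1.1 is zero by construction, and the randomized count promised in SAP 6.1 cannot be produced from dosed subjects. It would go too far to say that the exclusion counts as a whole are uninformative, because the PK Population block still works.
- **Comparability.** Overall discontinuation in Table 14.1.2.1 cannot be compared across columns. The recalled column can equal or exceed its fasted-only figure, but it cannot fall below it. Under equal assumed risks of 2% to 20% per period the expected excess is 2.0 to 16.0 points. It is larger if refusals are counted as non-completion, and zero if there is neither fed-period drop-out nor counted refusal. These rates are illustrations, because the documents supply none.

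The effect is on descriptive disposition and on how tolerability is read. No confidence interval or escalation decision changes.

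**What to change.** 1. Run Tables 14.1.1.1 and 14.1.2.1 and Listings 16.2.1.1, 16.2.1.2 and 16.2.3 on all randomized subjects, with rows for randomized and dosed. Amend SAP 3.1 and 6.1 to match. Because Protocol 10.4 frames disposition around dosed subjects, record the change in SAP 7.1.
2. In Table 14.1.2.1, report completion of the fasted period, through the Day 8 visit, for all dose levels and placebo.
3. Add a Fasted and Fed Cohorts disposition table in the style of Tables 14.1.3.2 and 14.1.7.2, showing who consented to recall, who was dosed fed, who completed Day 17, and reasons for not completing.
4. State that a subject who completes Day 8 and does not enter the fed period is a fasted-period completer.

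The cost is some SAP wording, one extra shell and a completion flag for each period. No subjects, visits or procedures are added.

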**3.2 Pharmacokinetic (PK) Population**

The Pharmacokinetic (PK) Population will consist of all subjects in the safety population who received at least one dose of ISLA101 and have a pre-dose PK sample and at least 1 post-dose analyzable PK sample (quantifiable Plasma concentration).

The following are reasons for exclusion from the PK Population:

- Subjects did not receive at least one dose of the ISLA101.
- Subjects did not have at least one quantifiable plasma fenretinide concentration.

Subjects will be analyzed according to the treatment they actually receive if this differs from that to which the subject was randomized. Adverse events (e.g., vomiting within 2 hours of dose), protocol deviations or dosing or sampling issues which may potentially impact PK will be assessed on a subject-by-subject basis.

Subjects with sufficient PK concentrations of fenretinide to allow determination of at least 1 PK parameter from ( $C_{max}$  or AUC) will be included in the PK parameters evaluations.

**3.3 Analysis of Subgroups**

No subgroup analyses are planned for this study.

**4. Study Measures**

This section describes the measures that were collected and/or derived during the study at the time points specified in the Schedule of Assessments (Section 2.5).

**4.1 Safety Measures**

The safety endpoints described in this section will be analyzed according to the analysis methods described in Section 6.8.

**4.1.1 Exposure to Study Drug**

Study drug administration information, including treatment administered (Yes/No), the date/time of last meal, high fat meal taken before dosing (Yes/No), the date/time of high meal consumed, the date/time

## Statistical Analysis Plan

**Sponsor:** Island Pharmaceuticals Ltd  
**Protocol Number:** ISLA101-P01-CT001

of the first capsule consumed, the dosage, the capsule administration quantity, the completion of all administered (Yes/No), the subject fasting for at least 4 hours post-study drug administration (Yes/No) and the calculated body surface area (BSA), will be reported on the 'Study Drug Administration' eCRF.

### 4.1.2 Adverse Events

An AE is the development of an undesirable medical condition or the deterioration of a pre-existing medical condition, regardless of whether it is considered casually related to the study treatment.

Adverse events data will be collected and recorded on the 'Adverse Events' eCRF from the time that informed consent was given and throughout the duration of the study.

Missing and partial AE dates will be handled according to the rules specified in Sections 5.1.4 and 5.6.2.

#### 4.1.2.1 Adverse Event Definitions

Treatment-emergent AEs (TEAEs) are defined as AEs occurring or worsening after the first administration of the study drug. If only partial information is available, the rules specified in Section 5.6.2 will be applied to determine treatment emergence.

Treatment-related AEs are defined as AEs where the relationship to study drug was reported as 'Possibly', 'Probably' or 'Definitely' Related or where the relationship is missing.

Serious AEs (SAEs) are defined as AEs where the events are reported as serious.

Severe AEs are defined as AEs where the event severity rating is reported as 'Severe'.

Adverse events leading to study drug discontinuation are defined as AEs where the action taken with study drug is reported as 'Drug Withdrawn'.

Adverse events leading to study discontinuation are defined as AEs where 'Other' action taken is reported as 'Withdrawn from study'.

#### 4.1.2.2 Coding of Adverse Event Terms

Adverse event terms (Investigator terms) will be coded to a lowest level term (LLT), preferred term (PT), high level term (HLT), high level group term (HLGT) and a system organ class (SOC) according to the Medical Dictionary for Regulatory Activities (MedDRA) dictionary, Version 26.1 or later, depending on the latest version available during the study.

### 4.1.3 Laboratory Evaluations

Laboratory evaluations will be performed in accordance with the Schedule of Study Assessments (Section 2.5). Blood and urine samples will be collected and analyzed by a local laboratory and the results of urinalysis will be reported on the 'Dipstick Urinalysis and Microscopy' eCRF and the result of hematology, coagulation, chemistry and microscopy will be provided in electronic format from the analyzing laboratory.

If the results for a specific laboratory test are not required by the study protocol (for example, only one subject has data for a specific test that was performed in error) or for urine microscopy tests that were only required in the presence of abnormal urinalysis results, the results will not be included in the summary tables, but the data will be listed.

The test panels and parameters presented in Table 2 will be collected and analyzed.

Parameter names will be based on the Clinical Data Interchange Standards Consortium (CDISC) Study Data Tabulation Model (SDTM) Controlled Terminology terms. The mapping of the reported parameter names to the standardized names will be presented in the SDTM specifications. Parameters will be sorted alphabetically.

